4.2 Conventions

Summary statistics will be presented for continuous variables, by way of number of subjects, mean, standard deviation (SD), median, first and third quartiles (Q1 and Q3, respectively), 5th and 95th percentiles (P05 and P95, respectively), minimum and maximum. For categorical variables including binary variables, counts and percentages will be presented. Percentages will be calculated using the total number of eyes in the respective column or the total number of eyes with an assessment, the total number of treated subjects, depending on the nature of the analysis.

In addition, 95% 2-sided confidence intervals (CIs) will be presented, where specified. The 95% CI of the mean value of an assessment will be calculated using the t-test formula. The 95% CI of the mean of change from baseline of an assessment will be calculated using the t-test formula. In case of percentages, the CI will be computed using the Clopper-Pearson method. (See [Section 4.21](#) for the corresponding SAS code).

No formal statistical comparison will be performed.

Summary statistics will be presented by period and overall for all endpoints. For selected endpoints (see details below), summary statistics will also be presented by Surgery Window (Short [<6 months], Medium [6-12 months] and Long [>12 months]) and overall. Where appropriate, summary statistics will be displayed by eye (SE1 and SE2), and by period.

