4.16.1 Visual Acuity

Best-corrected visual acuity (BCVA) and change from baseline will be summarised by visit, by eye, by period as well as overall. The corresponding 95% CIs will be calculated (See [Section 4.2](#)).

Furthermore, the proportion of eyes with a ≥ 10 letters increase, a ≥ 15 letters increase, and an increase or a loss < 5 letters (i.e. change from baseline > -5 letters) will be summarised by visit, by eye, by period as well as overall. The corresponding 95% CI will be presented (See [Section 4.2](#)).

The above main analyses will use the observed case method only. Imputation using LOCF method regardless of the reasons of missing data will be performed for supportive analyses (See [Section 4.8](#)).

In addition to the by-period, by-eye presentation mentioned above, as supportive analyses, for both continuous and categorical endpoints, the period 2 Study Eye 1 data will be presented by

remapping them to visits after their last visit in period 1 and calculating change from baseline using baseline at period 1 for the same eye (Study Eye 1). This way a full picture of Study Eye 1 treatment journey during the entire study will be presented.

For all assessments of periods 1 and 2 of Study Eye 1, the data records will be assigned to calculated visit window (using study day) as described in [Table 2](#) below. The window of the visits following baseline (including unscheduled visits) will be constructed in such a way that the upper limit of the interval falls half way between the two visits.

If a patient has more than one assessment included within a window, the assessment closest to the target day will be used. In case of ties between observations located on different sides of the target date, the value with the later date will be used.

Table 2 **Visit Assignment Windows**

Day / Month	Target Day	Day Range included in the visit
Baseline	0	The last assessment on or before day 0
Day 1	1	Day 1
Day 3	3	Day 2 to 5
Day 7	7	Day 6 to 10
Day 14	14	Day 11 to 22
Month 1	30	Day 23 to 61
Month 3	91	Day 62 to 136
Month 6	182	Day 137 to 272
Month 9	273	Day 228 to 318
Month 12	365	Day 319 to 410
Month 15	456	Day 411 to 501
Month 18	548	Day 502 to 593
Month 21	639	Day 594 to 684
Month 24	731	Day 685 onwards

Both continuous and categorical endpoints for BCVA will be summarised by subgroups mentioned in [Section 4.7](#).

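### SAP Table 2 ends the Month 6 window at Day 272 instead of Day 227, so it overlaps the Month 9 window by 45 days and one Study Eye 1 BCVA record can belong to two visits

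*SAP*

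**What the plan says.** SAP 4.16.1 (Visual Acuity) adds a supportive BCVA presentation to the by-visit, by-eye, by-period summaries. In it, the Period 2 data of Study Eye 1 (SE1) are placed after that eye's Period 1 visits and compared with its Period 1 baseline. The assignment rule is: "For all assessments of periods 1 and 2 of Study Eye 1, the data records will be assigned to calculated visit window", as set out in Table 2. The windows are to be built so that "the upper limit of the interval falls half way between the two visits".

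The two rows in question are:

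- Month 6: target day 182, Day 137 to 272
- Month 9: target day 273, Day 228 to 318

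There are two selection rules. The first is "If a patient has more than one assessment included within a window, the assessment closest to the target day will be used". The second is "In case of ties between observations located on different sides of the target date, the value with the later date will be used".

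**The concern.** The Month 6 window runs well into the Month 9 window, although the stated construction should give windows that meet without overlapping. Both selection rules choose between records inside one window. Neither chooses between two windows for one record.

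The remapped Period 2 visits of SE1 can land in the shared range. How each such record is reported then depends on how the code reads Table 2. A value may appear at two visits, or Month 9 may lose a value that belongs there. Either would distort the continuous and categorical BCVA results at Months 6 and 9 in the one presentation meant to show SE1 over the whole study.

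**Working it through.** **Inputs.** Target days and day ranges come from SAP Table 2. The visit schedule (Days 1, 3, 7 and 14; Months 1, 3, 6 and 12) and the ±14-day allowance at Months 3 and 6 come from Protocol 7.1 and Protocol Table 1.

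**1. Trying to reproduce the stated limit.** Half-way point = (target day + next target day) / 2. For Months 6 and 9 this is (182 + 273) / 2 = 227.5. Table 2 gives 272, which is 272 − 227.5 = 44.5 days later. Rounding up, rounding down or taking one day off does not give 272. Skipping Month 9, which is not a protocol visit, and using Month 12 (target 365) does not either: (182 + 365) / 2 = 273.5.

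**2. The same check on every row.**

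| Visit pair | Half-way point | Stated upper limit | Difference | Next window starts |
|---|---|---|---|---|
| Day 1 / Day 3 | 2.0 | 1 | −1.0 | 2 |
| Day 3 / Day 7 | 5.0 | 5 | 0.0 | 6 |
| Day 7 / Day 14 | 10.5 | 10 | −0.5 | 11 |
| Day 14 / Month 1 | 22.0 | 22 | 0.0 | 23 |
| Month 1 / Month 3 | 60.5 | 61 | +0.5 | 62 |
| Month 3 / Month 6 | 136.5 | 136 | −0.5 | 137 |
| **Month 6 / Month 9** | **227.5** | **272** | **+44.5** | **228** |
| Month 9 / Month 12 | 319.0 | 318 | −1.0 | 319 |
| Month 12 / Month 15 | 410.5 | 410 | −0.5 | 411 |
| Month 15 / Month 18 | 502.0 | 501 | −1.0 | 502 |
| Month 18 / Month 21 | 593.5 | 593 | −0.5 | 594 |
| Month 21 / Month 24 | 685.0 | 684 | −1.0 | 685 |

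Eleven of the 12 limits agree within one day and meet the next window exactly. The Month 9 limits themselves follow the rule, so the single wrong entry is the Month 6 upper limit.

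**3. Size of the overlap.** 272 − 228 + 1 = 45 days. The stated Month 6 window has 272 − 137 + 1 = 136 days, and 45/136 = 33%. The Month 9 window has 318 − 228 + 1 = 91 days, and 45/91 = 49%. All 45 days are nearer to 273 than to 182.

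**4. Can scheduled visits fall there?** Let *s* be the SE1 study day of the second-eye surgery. With visits on their target days, a Period 2 visit falls on Days 228 to 272 when:

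- Month 6 (*s* + 182): *s* = 46 to 90
- Month 3 (*s* + 91): *s* = 137 to 181
- Month 1 (*s* + 30) or one of the Day 1 to Day 14 visits: *s* = 198 to 271

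These are ordinary intervals within the short (<6 months) and medium (6-12 months) surgery windows.

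**5. Two ways the output goes wrong.**

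- *One value at two visits.* Take *s* = 45. The Period 2 Month 3 visit is on Day 45 + 91 = 136, in the Month 3 window. The Period 2 Month 6 visit is due on Day 45 + 182 = 227. If it is held one day late, within the ±14 days, it falls on Day 228. That is then the only scheduled record in both the Month 6 and the Month 9 window, so the same BCVA fills both.
- *A value lost.* Take *s* = 150. The Period 2 Month 1, 3 and 6 visits fall on Days 180, 241 and 332. If the code puts each record in the first row that matches, Day 241 goes to Month 6, loses to Day 180 (2 days from target against 59) and is dropped. Month 9 is empty, since Day 332 belongs to Month 12. With Month 6 ending at Day 227, Day 241 is the Month 9 value.

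**The case against.** The strongest reply is that the closest-to-target rule removes most double counting. Every day from 137 to 227 is at most 45 days from the Month 6 target, and every overlap day is at least 46 days from it. Any record on Days 137 to 227 therefore beats an overlap record for Month 6. In the *s* = 150 case, if Day 241 is admitted to both windows, Month 6 still takes Day 180 and Day 241 is used only at Month 9.

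With all visits on target there is always a scheduled record on Days 137 to 227: Period 2 Month 6 for *s* from 14 to 45, Period 2 Month 3 for 46 to 136, Period 2 Month 1 for 107 to 197, and Period 1 Month 6 for later surgery. Duplication then needs off-target or missed visits. As an illustration, assume that Period 2 Months 3 and 6 are each uniform over the 29 days of the ±14-day allowance and independent. The chance of a duplicate is ((60 − *s*)/29) × ((*s* − 31)/29). It is positive only for *s* = 32 to 59 and peaks at 15 × 14 / 841 = 25% at *s* = 45 or 46. So double counting is confined to a narrow range unless visits are missed.

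That argument stands, but it assumes that the code admits a record to both windows. If each record gets a single visit label, the loss at Month 9 follows instead, and the SAP does not say which approach applies. A careful programmer could infer Day 227 from the half-way rule and the Month 9 row, but the printed table contradicts that inference.

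The limits on scope also stand. Table 2 serves a supportive presentation of SE1 only, Month 9 is not a protocol visit, and the study makes no inference that could be affected: "No formal statistical comparison will be performed".

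**Conclusion.** The concern holds. The Month 6 upper limit is 44.5 days beyond the half-way point that the SAP prescribes, and 45 days belong to two windows. It is more than a clerical slip, because following the table as printed can give wrong or programmer-dependent results at Months 6 and 9.

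The impact is limited to the supportive whole-study SE1 BCVA presentation; the main observed-case summaries by visit, eye and period are untouched. The 33% and 49% are shares of window days, not of subjects or records. How many records are affected depends on the actual surgery intervals and visit dates, which the documents do not give. The 45-day overlap rests on Table 2 alone. The examples assume scheduled visits on or near target, and the lost-value case also assumes first-match coding. A transposition of 227 into 272 would explain the entry, but that is a guess and the conclusion does not depend on it. It should be corrected before the outputs are programmed.

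**What to change.** In SAP Table 2, change the Month 6 range to Day 137 to 227. The window then has 227 − 137 + 1 = 91 days, meets Month 9 at Day 228 with no gap or overlap, and agrees with the half-way rule in the text. The cost is one number in the SAP. No other row, no data collection and no protocol text needs to change.

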4.16.2 Fundus Autofluorescence

Observed value, change from baseline, and percent change from baseline for Total Area of Preserved AF, square root of the Total Area of Preserved AF and Distance from Foveal Center (FC) to nearest Border of Preserved AF will be summarised by visit, by eye, and by period.

The number and percentage of subjects with Subfoveal or non-Subfoveal Lesion in Relation to FC will be summarised by visit, by eye, and by period.

Shift from baseline in Lesion will be summarised by calculating the number of subjects falling in each of the following categories:

- Not subfoveal at Baseline to Not subfoveal
- Not subfoveal at Baseline to Subfoveal
- Subfoveal at Baseline to Not subfoveal
- Subfoveal at Baseline to Subfoveal

Those summaries will be presented by visit, by eye and by period.

For Subfoveal or non-Subfoveal Lesion in Relation to FC, 'Subfoveal' will be assigned as the 'worst case' value.

Image quality will be listed only. This includes image completeness, focus/clarity, field definition, exposure, contrast and 'Is the total area of preserved AF fully captured within frame'.

Note: The variable 'Distance from FC to nearest Border of Preserved AF' takes a positive value when 'Location of Lesion in Relation to FC' is Not Subfoveal and a negative value when 'Location of Lesion in Relation to FC' is Subfoveal.

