13.7.3 Fundus Autofluorescence

Total Area of Preserved AF and Distance from Foveal Center to nearest Border of Preserved AF, and their change from baseline, will be summarized by eye, period and visit.

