4.3 Definitions

Study Eye 1 (SE1) is defined as the first treated eye (within GEMINI or in an antecedent clinical trial). **Study Eye 2 (SE2)** is defined as the second treated eye (irrespective of whether the first eye was treated in GEMINI or in an antecedent clinical trial). Subjects whose first eye is treated in an antecedent study will contribute to Period 2 only (except for the immunogenicity analyses), where Study Eye 1 is the eye treated in the antecedent study and Study Eye 2 is the eye treated in GEMINI.

Period 1 starts on the day of the surgery of the first treated eye and ends on the day prior to the day of the surgery of the second treated eye. **Period 2** starts on the day of the surgery of the second treated eye.

Baseline Value of Period 1/2 is defined as the last non-missing value prior to treatment of the respective period. Baseline of each period for each eye will be used to calculate the change from baseline for the data in the same period and same eye. For example, period 1 SE1 baseline will be used to calculate the change from baseline for all the data of SE1 in period 1, whereas period 2 SE1 baseline will be used to calculate the change from baseline for all the data of SE1 in period 2.

For immunogenicity, baseline will be defined separately in [Section 4.17.11](#).

Analysis day for all the post-baseline visits will be calculated as the date of the post-baseline visits minus the corresponding injection date, depending on which baseline that was used.

For the 6 subjects whose first eye was treated in the antecedent study (Subjects [REDACTED], [REDACTED], [REDACTED]), only period 2 data are collected in GEMINI. Therefore, only period 2 data will be presented for these 6 patients.

Change from Baseline is defined as the difference of the value of an assessment at the considered visit from the baseline value of the corresponding period.

Duration is measured in days and is calculated as end date – onset date + 1.

Injection dates of SE1 and SE2 will be coded **Day 0** for the Period 1 and Period 2 respectively.

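### Percent change from baseline is planned for a signed foveal distance that is negative in subfoveal eyes, so worsening can be reported as a positive percentage

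*SAP*

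**What the plan says.** SAP 4.16.2 lists three AF variables in one sentence: total area of preserved AF, its square root, and the foveal distance. The sentence opens with "Observed value, change from baseline, and percent change from baseline for Total Area of Preserved AF" and closes with "square root of the Total Area of Preserved AF and Distance from Foveal Center (FC) to nearest Border of Preserved AF will be summarised". All three therefore get observed value, change and percent change, by visit, eye and period.

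The note at the end of that section fixes the sign of the distance. It is positive when the lesion "is Not Subfoveal and a negative value when" the lesion is subfoveal. The section also treats subfoveal as the worst case, so a lower or more negative distance is worse. Its shift table has two rows for eyes already subfoveal at baseline, so negative baselines are expected.

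SAP 4.3 defines change from baseline as the "difference of the value of an assessment at the considered visit from the baseline value of the corresponding period". It does not define percent change. SAP 4.21 gives code for summaries and confidence intervals but none for percent change. No rule covers a negative, zero or near-zero baseline.

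Protocol 13.7.3 asks for the total area and the foveal distance, "and their change from baseline, will be summarized by eye, period and visit". It does not ask for percent change, and SAP 4.20 does not list percent change among the changes from the protocol.

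**The concern.** Percent change is meaningful for a quantity that is always positive and has a real zero. The foveal distance is not of that kind: its zero is only the point at which the border of preserved AF lies at the foveal centre, and eyes can lie on either side of it. Dividing by a negative baseline reverses the direction of the result, and dividing by a small baseline inflates it without limit.

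AF is a listed safety measure and change in AF is a secondary efficacy endpoint. SAP 4.17.7 sends the safety reporting of AF back to this same analysis. Under SAP 4.2 the output includes the mean, SD, median, quartiles, 5th and 95th percentiles, minimum and maximum, so the affected values go into reported tables. At worst, the mean percent change suggests a gain when every eye has moved in the wrong direction.

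**Working it through.** The plan states no figure to reproduce. The sign convention and the direction of worsening come from SAP 4.16.2. The distances below are illustrative assumptions in whatever unit is recorded.

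**Formula.** The SAP gives none, so I use the usual one: percent change = 100 × (value − baseline) / baseline.

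**Single eyes**

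| Baseline | Visit | Direction | Change | Percent change |
|---|---|---|---|---|
| 200 | 100 | worse | -100 | -50% |
| 200 | 300 | better | +100 | +50% |
| -200 | -300 | worse | -100 | +50% |
| -200 | -100 | better | +100 | -50% |
| 200 | -100 | worse, crosses fovea | -300 | -150% |
| -200 | 100 | better, crosses fovea | +300 | -150% |
| -10 | -110 | worse, near zero | -100 | +1000% |
| 10 | -90 | worse, near zero | -100 | -1000% |

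Absolute change has the right sign in every row. Percent change has the wrong sign in every row with a negative baseline.

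**A group in which every eye worsens by 100.** Let a share f start at -200 and the rest at +200. The mean percent change is −50(1 − f) + 50f = 100f − 50.

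| f | 0% | 10% | 25% | 50% | 75% | 100% |
|---|---|---|---|---|---|---|
| Mean percent change | -50% | -40% | -25% | 0% | +25% | +50% |

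The mean absolute change is -100 throughout.

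**A few near-zero baselines.** Suppose 57 eyes go from 200 to 100 and 3 go from -10 to -110. The mean is (57 × (−50) + 3 × 1000) / 60 = 150 / 60 = +2.5%, although all 60 eyes worsened. With only one such eye it is (59 × (−50) + 1000) / 60 = -32.5%.

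**Simulation.** 60 eyes, normal baseline with SD 400 (rounded), every eye worsening by exactly 50, 5,000 repeats. The expected share of eyes with a negative baseline is Φ(−mean/400).

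| Assumed baseline mean | Eyes with wrong sign | Repeats with positive mean percent change |
|---|---|---|
| 300 | 23% | 30% |
| 500 | 11% | 20% |
| 800 | 2% | 8% |
| 1200 | 0.1% | 1% |

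At a mean of 300, the 5th, 50th and 95th percentiles of the mean percent change were -59.4%, -8.0% and +42.2%. A second set of random draws gave an upper limit of +45% and a positive mean in 31% of repeats, which is within simulation error. At the same setting the median percent change was never positive (5th to 95th percentile -11.7% to -7.4%), and the third quartile was positive in 29% of repeats. At a mean of 500 the third quartile was positive in 0.06%. The absolute change is -50 for every eye in all settings.

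**The case against.** The strongest reply is that little depends on this block. SAP 4.16.2 already gives the observed value and absolute change of the same distance, the counts of subfoveal eyes and the shift table. Total area and its square root cannot be negative, so their percent change keeps the right sign. No comparison is tested, and the section plans no confidence interval for AF. A reader can find the correct direction nearby. All of this stands, and it limits the seriousness of the point.

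Second, the mean is the most fragile statistic. The median keeps the right sign while negative baselines are a minority. That also stands. But when every eye worsens, the third quartile goes wrong once about a quarter of eyes have a negative baseline, the 95th percentile once about 5% do, and the maximum with a single such eye. The mean and SD can be dominated by one or two eyes near zero.

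Third, the size rests on an assumed baseline distribution and shrinks quickly as baselines move away from zero. This is correct, and it is why the table runs from 300 to 1200.

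Fourth, the SAP does not state the formula, and dividing by the absolute value of the baseline would restore the sign. The SAP does not say it does this, and the instability remains: -10 to -110 would be -1000%.

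Finally, Protocol 13.4 leaves detailed specification to the SAP, so adding percent change is not in itself an error. I agree. The fault is in applying it to this variable.

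**Conclusion.** The point holds. By the SAP's own sign convention and the usual formula, percent change for the foveal distance reverses direction in every eye with a negative baseline, is undefined at zero and is unstable near zero. Nothing in SAP 4.3, 4.20 or 4.21 prevents this.

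How far the reported mean would be distorted cannot be known from the documents, because they give neither the distribution of the distance nor the share of eyes subfoveal at baseline. Under the assumptions shown, the chance that the mean points the wrong way when every eye worsens runs from about 1% (baseline mean 1200) to about 30% (baseline mean 300). If no eye had a negative or near-zero baseline, the mean would be interpretable.

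The damage is limited to one untested descriptive block. The analysis should be corrected before the tables are produced, but no conclusion of the trial rests on it.

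**What to change.** In SAP 4.16.2, split the sentence. Keep observed value, change and percent change for the total area of preserved AF and its square root. For the distance from the foveal centre to the nearest border of preserved AF, keep observed value and absolute change only. Leave the subfoveal counts and the shift table as they are, since they show which eyes cross the fovea.

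Two small additions would help. Define percent change in SAP 4.3, where it is now missing, and record in SAP 4.20 that percent change is an addition to Protocol 13.7.3 for the variables that keep it.

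The cost is one clause in the SAP and one fewer block in the AF table. No valid information is lost, and no data collection changes.

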4.8 Handling of Missing Values

The number, pattern and timing of missing data will be examined along with the reasons for withdrawal or for missing data.

The safety analyses will be performed using the ‘observed case’ method. In the efficacy analysis, observed case method will be applied as main analysis for categorical and continuous endpoints. The following supportive analysis will be performed for BCVA related endpoints: both categorical endpoints and continuous endpoints will be imputed using the ‘Last Observation Carried Forward’ (LOCF) method with the last available measurement prior to missing (see details in [Section 4.16.1](#)).

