4.17 Safety Analysis

Safety analysis will be performed on the All Treated Subjects analysis set using observed cases only.

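### The flag for incompletely framed autofluorescence images is only listed, so any area recorded from such an image enters the change summaries without qualification

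*SAP*

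**What the plan says.** For each visit of each period, and separately for each eye, Protocol 13.7.3 plans that "Total Area of Preserved AF and Distance from Foveal Center to nearest Border of Preserved AF, and their change from baseline, will be summarized". SAP 4.16.2 widens this to the observed value, "change from baseline, and percent change from baseline for Total Area of Preserved AF", and does the same for the square root of the area. Neither section sets an image-quality condition.

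SAP 4.16.2 then states: "Image quality will be listed only". Among the items so listed is "Is the total area of preserved AF fully captured within frame".

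The general rules do not fill the gap:

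- SAP 4.2: "Summary statistics will be presented for continuous variables, by way of number of subjects, mean, standard deviation (SD), median", followed by quartiles, outer percentiles and extremes.
- SAP 4.3: baseline is the latest recorded value before treatment in that period, with no quality requirement.
- SAP 4.8: "In the efficacy analysis, observed case method will be applied as main analysis for categorical and continuous endpoints". LOCF support is planned for BCVA only.
- SAP 4.17: "Safety analysis will be performed on the All Treated Subjects analysis set using observed cases only". SAP 4.17.7, on AF as a safety measure, only points back to 4.16.2.
- SAP 4.20, on departures from the protocol, does not mention AF.

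The worst-case rule in SAP 4.16.2 concerns lesion location, not area.

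**The concern.** Most image-quality items, such as focus or contrast, bear on how precisely the area is measured. The capture item says whether the measured quantity is the endpoint at all. If part of the preserved region lies outside the frame, the recorded figure is a minimum for the total area.

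The change from baseline then mixes tissue change with framing. A truncated baseline followed by a complete image reads as gain of viable retina, and the reverse reads as loss. Because each eye has one baseline per period, a truncated baseline carries through to every later visit of that period.

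Change in AF is one of four secondary efficacy endpoints, and AF is one of ten safety measures (SAP 2.2). Protocol 11.8 gives the purpose of AF imaging as following the area of viable retina, so a framing artefact would be read directly as the outcome of interest.

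**Working it through.** **No figure to reproduce.** The documents give no target, assumed effect or sample-size calculation for AF. The check is of the text, followed by an illustration.

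**Text.** SAP 4.2, 4.3, 4.8, 4.16.2, 4.17, 4.17.7 and 4.20 and Protocol 11.8 and 13.7.3 were compared. None excludes a flagged area, sets it to missing, treats it as a lower bound, limits change to fully captured pairs or plans a sensitivity analysis. By contrast, SAP 4.17.11.3 does say that invalid immunogenicity results count as missing. AF area has no such sentence.

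**Illustration: inputs.** Both are assumptions, because the documents give neither.

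- f, the share of eyes flagged: 5% to 30%
- t, the share of true area outside the frame in a flagged eye: 5% to 20%

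**Formulas, with true change zero.**

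- Follow-up truncated only: the eye reads (1 - t) - 1 = -t, so the mean shifts by -f × t.
- Baseline truncated only: the eye reads 1/(1 - t) - 1 = t/(1 - t), so the mean shifts by +f × t/(1 - t).
- Square-root area, follow-up truncated only: the mean shifts by -f × (1 - √(1 - t)).

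**Shift in mean percent change (percentage points).**

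| f | t | Follow-up only | Baseline only | Square root, follow-up only |
|---|---|---|---|---|
| 5% | 5% | -0.25 | +0.26 | -0.13 |
| 10% | 10% | -1.00 | +1.11 | -0.51 |
| 20% | 20% | -4.00 | +5.00 | -2.11 |
| 30% | 20% | -6.00 | +7.50 | -3.17 |

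Worked line for the last row: 0.30 × 0.20 = 6.0 points down; 0.30 × 0.20/0.80 = 7.5 points up.

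**Cancellation.** If 10% of eyes are truncated at follow-up only and another 10% at baseline only, each by 10%, the net shift is -1.00 + 1.11 = +0.11 points. The mean is then nearly right, but the individual values are still wrong.

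**Both visits truncated.** Take a true area of 100 falling to 90, with 20 outside the frame at each visit. If all the loss is inside the frame, the reading goes from 80 to 70, or -12.5%. If all the loss is outside, it stays at 80, or 0%. The true change is -10%.

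**The case against.** The strongest reply is that the bias may never arise. Protocol 11.8 leaves AF measurement to reading-centre procedures in the Study Operations Manual. If the centre does not report an area when the frame is incomplete, the value is missing and drops out under the observed-case rule. This stands. A reader might infer from SAP 4.16.2 that truncated areas certainly enter the means as if complete, but the documents do not support that. A separate yes/no capture item beside the area suggests that a value can exist with the answer no, which is inference only.

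A reader might also infer that eyes with early disease and large preserved areas are the ones affected, since inclusion sets no upper acuity limit. The documents give no field size, no typical preserved area and no share of flagged images, so this is unsupported. Protocol 9.4 points somewhat the other way: it uses AF to locate the boundaries of surviving tissue at surgery, which presumes that they can normally be seen.

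The consequences are limited too. No formal comparison is planned. Medians and quartiles accompany the means. Distance to the nearest border and subfoveal location are central measures that the frame edge hardly touches. The flags are listed by subject, eye and visit (SAP 5.2), so affected eyes can be traced. Tracing, however, does not give the reader a summary without them.

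Finally, restricting to fully captured pairs could selectively remove eyes with large areas. This is a fair reason not to replace the all-images summary, but not a reason to omit the restricted one.

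**Conclusion.** The point holds in a limited form. The SAP plans to hold an item that says whether the recorded area is a total, and uses it in no summary. It states no rule for areas recorded when the answer is no. Any such area would be treated as complete.

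Under the assumed ranges, the shift in mean percent change runs from about -6.0 to +7.5 points. Its sign depends on which visit is truncated, and opposite errors partly cancel. A reading that the tables will show false regrowth, or false loss, goes further than the documents allow. Neither the frequency nor the direction of truncation can be derived from them.

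The effect is confined to total area and its square root, and no test or sample size is touched. The point is still worth acting on, because readers could not correct the summaries themselves and the item needed is already planned for listing.

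**What to change.** In SAP 4.16.2:

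1. Report the number of eyes flagged as not fully captured, by visit, eye and period, including baseline.
2. Add a summary of change and percent change in Total Area of Preserved AF and its square root, restricted to eyes fully captured at both baseline and the visit. Show it beside the all-images summary.
3. If the reading centre already sets such areas to missing, state that in one sentence in place of items 1 and 2.

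The cost is a short addition to the text and one repeat table, with no new data. The restricted set will have fewer eyes, may change from visit to visit and may under-represent eyes with large preserved areas. The two versions should therefore be read together.
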